7.2.2.3. Other potential adverse events

Monitoring

Numerous other adverse events are expected. Specific symptoms and lab abnormalities likely to occur will be systematically monitored at each visit using detailed questions in the CRF.

Management

They will be managed according to guidelines by the site investigators. Multiple resources are available on the internet, for example "Hepatitis C Treatment Side Effects Management Chart" of the US Department of Veterans Affairs (<http://www.hepatitis.va.gov/products/patient/side-effects-chart.asp>). The protocol team, including experienced hepatologists from Thailand and France, will be consulted if necessary. Recommendations for the management of clinical side effects of the treatment are described in the Appendix 4.

7.2.3. Implementation

Roles of protocol team members, investigators and co-investigators

The PHPT Clinical Trial Unit (CTU) team is responsible for the overall organization and monitoring of the study, as well as data entry, data management and statistical analysis in compliance with Good Clinical Practices and, as necessary, reporting to sponsors. The technical team in charge of the study at the CTU will be composed of 1 physician, 1 coordinator, 1 nurse in charge of the safety monitoring, at least 4 clinical research assistants, 1 data manager, 3 data entry technicians, 1 laboratory technician, 1 logistician, 1 translator and 1 secretary. In addition, the PHPT CTU pharmacist will oversee the management of study drugs.

The protocol team is responsible for the design of the study, the preparation of the study and its monitoring. Members of the protocol team are not involved in the day to day patient management but may provide suggestions to site investigators in relation with the conduct of the study.

Site co-investigators are responsible for the medical management of the patients, the implementation of the study interventions according to the protocol and the completion of the Case Report Forms (CRFs). At each site, the study teams consist of internists who will implement the study in close collaboration with gastroenterologists, nurses, laboratory technicians, pharmacists and counselors. Study co-investigators and study staff will be trained before the beginning of and during the study to the specific aspects of Hepatitis C treatment management.

The PHPT laboratory staff also monitors the quality control of the site laboratories.

7.2.4. Data collection

The completed CRFs are reviewed and signed by the site co-investigator, then forwarded to the CTU. Upon arrival at the CTU, they are immediately recorded in a tracking database and filed. The tracking database provides updated information on each patient every week, as well as the total number of patients at each stage of follow-up.

Data will be keyed using a double data entry system, and programs check the datasets for range checks on each field within a form, consistency checks between fields on the same form, and between fields on different forms. The data managers generate queries as necessary until final validation of the CRFs. Validated CRFs serve as evidence that the history and clinical data has been recorded, and that all lab tests and procedures have been completed. All serious adverse events will be reported according to GCP. As required by GCP, any change made to an original CRFs/data set is documented. The databases are stored in My-SQL format in central computers with restricted access and regular backups are made and stored in another place to prevent accidental loss of data. All important operations are described in procedures within our IRD UMI 174 quality management system, accredited according to the standard of ISO 9001:2008.

As for previous studies conducted by our group, investigators and co-investigators will facilitate any audit of the data, procedures at study sites and at the laboratory by independent external monitors sent by sponsors.

The PHPT laboratory staff also monitors the quality control of the site laboratories.

7.2.5. Laboratory assessments

The PHPT laboratory is responsible for the centralized laboratory exams, i.e., HCV RNA quantification, IL-28 polymorphism, ribavirin level, HIV viral load, and samples repository. The blood samples will be stored until the completion of the study, two years after the date of last study visit for repeated/confirmation assessments if needed. The PHPT laboratory is located in Chiang Mai, under the Faculty of Associated Medical Sciences, Chiang Mai University.

The PHPT laboratory has received the laboratory accreditation by the Association of Medical Technologists of Thailand (AMTT) and the ISO 15189 accreditation by the DMSc, MoPH, Thailand.

HCV RNA load will be measured at the central PHPT laboratory using the commercial Abbott RealTime HCV (Abbott Laboratories) assay. Performance will be controlled through participation in the Quality Control for Molecular Diagnostics (QCMD, Scotland, UK) external quality assessment program for HCV RNA. Other laboratory evaluations will be performed at the site laboratories.

7.3. Study drugs

Peg-interferon alpha 2-b

First dose: 1.5 micrograms/kg (subcutaneous injection)

Mode of administration:

The study nurse will read with each patient the booklet 'Patient diary for PEG-INTRON monotherapy or PEG-INTRON and Rebetol' in Thai language (MSD), which provides information on peg interferon and ribavirin and specific instructions for the preparation and injection of peg-interferon. The nurse will give each patient this booklet.

For the first injection, the study site nurse at the hospital will prepare the syringe and proceed to the injection, observe and record the occurrence of side effect for at least the first 3 hours after administration. The second injection, one week later, can be done by the patient, under supervision of an experienced nurse at the hospital. The nurse will evaluate if the patient is able and willing to perform following injections by him/herself. As long as the patient does not appear able or willing to perform injections, he/she will be welcome to return to the hospital for injections.

The patient will be provided with an Injection Card, reporting all the injections received with date, time and person who administered the dose. During the first weeks, the nurses will regularly call the patient to make sure that the drugs are correctly administered and how to deal with adverse events.

Ribavirin

First dose:

- For genotypes 2, 3: ribavirin 400 mg in the morning and in the evening (i.e. 800 mg daily).
- For genotypes 1, 4, 5 and 6: the ribavirin dose is
 - 800 mg/day, if bodyweight <65 kg,
 - 1000 mg/day, if bodyweight between 66–80 kg,
 - 1200 mg/day, if bodyweight between 81–105 kg,
 - 1400 mg/day, if bodyweight >105 kg.

Mode of administration:

Ribavirin should be given in two divided doses (e.g. 400/400 mg bid, 600/400 mg bid, 600/600 mg bid, or 800/600 mg bid) at the end of the meals, in the morning and evening.

At each visit, patients will be asked to bring back the remaining study drug's vials or bottles (Peg-interferon alpha 2-b and ribavirin) even if they are empty to assess adherence.

The study site pharmacist will be responsible for storage, dispensation including drug counseling, and drug accountability.

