[name],
[name]
[contact]
[contact], [name]
E-mail: [contact]

Sanpatong Hospital

[name]
Internal Medicine Department
Sanpatong Hospital
[name]
[contact], [name]-
[contact]
Email: [contact]

3. Project Summary

Title: Response to peg-interferon and ribavirin for the treatment of HCV infection in HIV co-infected patients, implemented in public hospitals in Thailand

This is a study of HCV treatment using the standard regimen of pegylated-interferon plus ribavirin in HIV co-infected patients participating in the PHPT cohort study. The treatment will be implemented in conjunction with gastro-enterologists/hepatologists by the internists responsible for the HIV treatment.

Chronic hepatitis C virus (HCV) infection is responsible for several severe and life threatening complications, which are worsened by HIV co-infection. HIV-HCV co-infected patients are at a higher risk of death compared to HIV mono-infected individuals, even if HIV replication is suppressed on antiretroviral treatment.

The goal of HCV antiviral treatment is to cure HCV infection. Curing HCV infection allows fibrosis regression, improved clinical outcomes. In addition, individuals who have been cured are no longer contagious to other individuals, therefore widespread access to HCV treatment may contribute to the control of the HCV epidemic.

A combination of injectable pegylated-interferon with oral ribavirin is currently the recommended regimen for the treatment of hepatitis C in the setting of HIV co-infection. They are administered for 24 weeks in HCV mono-infected patients but need to be administered for one year in HIV-HCV co-infected patients. Newer drugs, such as the first generation HCV protease inhibitors (boceprevir, telaprevir), administered concomitantly, are used in patients who have not been cured using peg-interferon + ribavirin, or may allow for a shorter treatment.

PRIMARY OBJECTIVE

1. To determine the percentage of patients according to genotypes with sustained virological response 6 months after treatment discontinuation (SVR).

HCV TREATMENT

- Peg-interferon alpha 2-b (a subcutaneous injection of 1.5 micrograms/kg once a week)
- Ribavirin dosing according to HCV genotype and bodyweight; dose adjustment in case of anemia.

SAMPLE SIZE

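### Section 7.3 assigns no ribavirin starting dose at 65 kg for genotypes 1, 4, 5 and 6, and leaves a second gap at 80–81 kg if weights carry decimals (wrong as written; minor)

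*Combined protocol and SAP*

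**What the plan says.** Section 7.3 (Study drugs, Ribavirin, first dose) gives genotypes 2 and 3 a flat 800 mg daily. The weight rule is introduced by "For genotypes 1, 4, 5 and 6: the ribavirin dose is" and has four bands:

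- The lowest band reads "800 mg/day, if bodyweight <65 kg".
- The second band starts a kilogram higher and reads "1000 mg/day, if bodyweight between 66–80 kg".
- The third band runs from 81 to 105 kg, at 1200 mg/day.
- The top band takes every weight above 105 kg, at 1400 mg/day.

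The only other statement on the starting dose is in the Project Summary: "Ribavirin dosing according to HCV genotype and bodyweight; dose adjustment in case of anemia". It gives no limits and no rounding rule. Section 7.2.2.1 and the laboratory tables in Appendix 4 deal with dose reduction, not with the first dose. Tables 2, 3 and 4 set no limit on bodyweight, so a patient of any weight can be eligible. I found no row for bodyweight in Tables 5 and 6, so they supply no recording convention either.

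**The concern.** A dosing rule should return exactly one dose for every eligible patient. This one returns none at 65 kg and, depending on how weight is recorded, none just above 80 kg. A site that follows the protocol faithfully has nothing to follow for such a patient. Two sites could give similar patients doses 200 mg/day apart without either one deviating from the protocol.

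The starting dose also fixes where the patient enters the reduction sequence. It therefore bears on how many reductions are possible before ribavirin is stopped. That matters for secondary objective 5 (premature discontinuation for tolerance or safety) and secondary objective 6 (ribavirin concentration and its relation to anemia). The banded genotypes are not a rare branch: section 4.2 names genotypes 3 and 6 as predominant in Southeast Asia, and genotype 6 is dosed by weight.

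**Working it through.** **Step 1: which weights are covered.** Take the bands literally, with w the bodyweight in kg: w < 65; 66 ≤ w ≤ 80; 81 ≤ w ≤ 105; w > 105. Checking every weight from 30.0 to 130.0 kg in 0.1 kg steps gives:

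| How weight is recorded | Weights with no band |
|---|---|
| Decimals, no rounding | 65.0–65.9 kg and 80.1–80.9 kg |
| Rounded half-up to whole kg | true weight 64.5–65.4 kg (recorded as 65) |
| Truncated to whole kg | true weight 65.0–65.9 kg (recorded as 65) |

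No weight falls in two bands, and the third and fourth bands meet at 105 kg. The 65 kg gap survives every convention tried. The 80–81 kg gap exists only with decimals.

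**Step 2: how many patients.** The documents give no weight distribution, so this step rests on assumption. Suppose weight is normal with mean m and SD s. The share in an interval (a, b) is Φ((b − m)/s) − Φ((a − m)/s).

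| Assumed m / s (kg) | 65–66 kg | 80–81 kg | Sum | × 60 patients |
|---|---|---|---|---|
| 55 / 9 | Φ(1.222) − Φ(1.111) = 2.24% | 0.08% | 2.3% | 1.4 |
| 58 / 10 | Φ(0.8) − Φ(0.7) = 3.01% | 0.32% | 3.3% | 2.0 |
| 62 / 11 | Φ(0.364) − Φ(0.273) = 3.45% | 0.88% | 4.3% | 2.6 |

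The last column supposes that all 60 patients have genotype 1, 4, 5 or 6, so it is an upper bound within each scenario. If half did (a further assumption) and only the 65 kg gap counted, the number would be 60 × 0.5 × 2.24% = 0.7 to 60 × 0.5 × 3.45% = 1.0. For the 15 patients of the first part, the same product is 0.2 to 0.3.

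**Step 3: what differs across a gap.** The doses on either side of 65 kg are 800 and 1000 mg/day. The difference of 200 mg is 25% of the lower dose (200/800) or 20% of the higher (200/1000). Across 80–81 kg they are 1000 and 1200 mg/day, again 200 mg apart.

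**Step 4: reduction steps.** In the Appendix 4 sequence, written as morning/evening mg:

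- from 800: 400/400 → 400/200 → stop (one reduction)
- from 1000: 600/400 → 400/400 → 400/200 → stop (two)
- from 1200: 600/600 → 600/400 → 400/400 → 400/200 → stop (three, though the appendix asks sites to make contact if abnormalities persist after two)

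The stepwise rule in section 7.2.2.1 also gives one reduction from 800 and two from 1000 before its 600 mg/day floor. At 65 kg, then, both passages make the number of available reductions depend on a starting dose that the protocol does not define.

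**The case against.** The strongest reply is that this is a drafting slip. The limits are in whole kilograms. Read that way, 80 and 81 kg are adjacent and both covered, and moving one of the two limits around 65 kg would complete the scheme. That stands in part: the 80–81 kg gap is conditional on decimal weights, and the two gaps should not be treated as equals. It does not remove the gap at 65 kg, which is present in whole kilograms too.

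The reply also holds that very few patients are involved and that help is at hand. Section 7.2.3 lets the protocol team make suggestions to sites and puts the CTU pharmacist in charge of overseeing study drugs. A reader might infer from Table 1 that 12 sites would each settle on a dose of their own. The documents do not support that: only 7 sites are listed for the first part, most sites would never meet such a patient, and central advice is available. That advice does not supply the missing rule, however.

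Finally, the study is a single group with no arm comparison to bias. Ribavirin levels are measured at weeks 2 and 4, section 7.4.1 calls the ribavirin concentration analysis descriptive, and anemia management already moves doses by 200 mg. A reader might still infer that the primary SVR result is at risk. It is not, to any useful degree: section 7.4.2 quotes an interval of 47% to 72% for a 60% rate in 60 patients, and one or two patients at an adjacent dose would be lost in that width.

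**Conclusion.** The dosing rule is wrong as written, and the severity is minor. A genotype 1, 4, 5 or 6 patient recorded at 65 kg has no assigned starting dose under any recording convention checked. That conclusion rests on the text alone. The 80–81 kg gap holds only if weights are recorded with decimals, on which the documents are silent.

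The number affected rests on the assumed weight distributions. It is at most about 1–3 of 60, and probably about one or fewer once patients on the flat genotype 2 and 3 dose are set aside. Only the first 15 patients are certain, since the other 45 depend on funding.

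What remains is an undefined study-drug dose. For the patients concerned it can shift ribavirin exposure, and with it the anemia and discontinuation outcomes of objectives 5 and 6.

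**What to change.** In section 7.3, reconcile the limits of the weight bands so that every bodyweight falls in exactly one band, and state how bodyweight is rounded before the band is read. Which dose applies at each limit is for the clinical team to decide. The cost is a one-line protocol correction, submitted for ethics approval like any other modification (section 8.3.1), and a memo to sites. Sample size and analyses are unchanged.

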7.4 Statistical considerations

Considering the proportion of HCV circulating genotypes in Thailand and the high proportion of Asian people with IL28B CC polymorphism, it is expected that up to two thirds of the patients may be cured of their HCV infection.

7.4.1. Endpoints

For each objective, the following definitions of endpoints will be used:

Primary objective 1: To assess the percentage of patients according to genotypes with sustained virological response 6 months after treatment discontinuation (SVR).

The SVR is the percentage of patients with sustained virological response among the patients who have taken at least one dose of HCV treatment.

Secondary objective 2: To assess the safety of HCV treatment: incidence of serious adverse events as defined by ICH GCP ("International conference on harmonization (ICH) Good Clinical Practice (GCP)," 1996).

The cumulative risk of any serious adverse event will be assessed 6, 12 and 18 months after HCV treatment initiation using a Kaplan-Meier curve. The distribution of serious adverse events will be provided by type of events (in particular hematology, central nervous system).

Secondary objective 3: To report on operational issues.

Operational issues will be described and documented to serve as a source of information for further HCV treatment implementation. Specific endpoints will include: the proportion of patients screened and enrolled in the study who have completed the first 24 and 48 weeks of treatment, incidence of adverse events by severity grade, compliance with study visit schedule, adherence to HCV and HIV

treatment (peg-interferon injections, number of missed doses of oral treatment during the last week, pill count), number/percentage of patients able to perform self-injections.

Secondary objective 4: To assess the percentage of patients with early virological response at week 12 of treatment (EVR).

The EVR is the percentage of patients with early virological response among the patients who have taken at least one dose of HCV treatment.

Secondary objective 5: To assess the risk of premature treatment discontinuation for tolerance or safety reasons.

The cumulative risk of premature HCV treatment discontinuation will be assessed using a Kaplan-Meier curve.

Secondary objective 6: To assess the plasma concentrations of ribavirin in Thai patients. The analysis will be descriptive. Ribavirin trough plasma concentration will be determined and compared to published data in non-Asian populations.

Secondary objective 7: To assess the impact of HCV treatment on HIV infection. HIV viral load will be monitored.

Secondary objective 8: To assess the effect of the treatment on quality of life. The score provided by SF-36 will be used as a measure of the quality of life.

7.4.2. Sample size

We recognize that the small number of study participants, i.e. 15 in a first part and, if possible, an additional 45 patients in a second part, is due to funding considerations rather than statistical considerations. The precision of the estimate will be limited. For example, the 95% confidence interval (CI) of a 60% SVR rate in a group of 60 patients is 47% to 72%. Higher rates would have a narrower CI. With 60 subjects, there would be 71% power to conclude that an observed SVR rate of 66% is significantly greater than 50% in a two-sided exact binomial test of nominal type I error of 5%.

However, no data are currently available on HCV treatment in the HIV infected population in Thailand, and data carefully collected from this relatively small number of patients undergoing treatment will help better understand feasibility issues

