- Ophthalmologic examination if diabetes mellitus or hypertension
- CBC
- Electrocardiogram
- Chest X-ray
- Creatinine, urine protein
- Beck's Depression Inventory
- Pregnancy test (for female participant or partner of male participant) if childbearing age
- IL28B polymorphism.

After HCV treatment initiation, patients will be monitored for safety and antiviral efficacy at 2, 4, 8, 12, 16, 20, 24, 28, 32, 36, 40, 44 and 48 weeks (end of treatment) and 6 months after treatment discontinuation.

Treatment will be discontinued earlier in patients who do not achieve early viral response, i.e. a decrease of at least 2 log₁₀ HCV RNA IU/mL after the first 12 weeks of HCV therapy.

DURATION OF THE STUDY

First enrollment: April 2014

Planned enrollment duration: until April 2015

Planned date of last visit completed: November 2016

Biological analyses completed: November 2017

Final analyses and submission of manuscripts: November 2018

STATISTICAL CONSIDERATIONS

It is expected that up to two thirds of the patients will be cured of their HCV infection. With 60 subjects, there would be 71% power to conclude that an observed SVR rate of 66% is significantly greater than 50% in a two-sided exact binomial test of nominal type I error of 5%.

All patient characteristics recorded at baseline will be summarized using frequencies, medians and confidence intervals. All endpoints will be summarized using appropriate statistical methods. Details on these analyses will be further provided in the statistical analysis plan before their initiation.

4. Background information

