7.4.5. Analyses

All patient characteristics recorded at baseline will be summarized using frequencies, medians and confidence intervals.

All endpoints will be summarized using appropriate statistical methods.

Details on these analyses will be further provided in the statistical analysis plan before their initiation.

8. Ethical considerations

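### The stated 71% power is not the power of the two-sided exact binomial test named for it; with 60 patients and a true SVR rate of 66% that test has 62% power

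*Combined protocol and SAP*

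**What the plan says.** Section 7.4.2 (Sample size) gives one power statement, for 60 subjects: "71% power to conclude that an observed SVR rate of 66% is significantly greater than 50% in a two-sided exact binomial test", at a nominal 5% type I error. The Statistical considerations part of the Project Summary (Section 3) makes the same claim: "With 60 subjects, there would be 71% power to conclude that an observed SVR rate of 66% is significantly greater than 50"%.

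Three other statements bear on how much weight the figure carries:

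- Section 7.4 gives the basis for the assumed rate: "it is expected that up to two thirds of the patients may be cured of their HCV infection".
- Section 7.4.2 says that the number of participants "is due to funding considerations rather than statistical considerations". As an example of precision it gives a 95% confidence interval of 47% to 72% for a 60% SVR rate in 60 patients.
- Section 7.4.5 commits to no particular test: "All endpoints will be summarized using appropriate statistical methods", with details left to a later analysis plan.

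**The concern.** The sentence fixes everything needed to recompute its power: sample size, null rate, alternative rate, test, sidedness and significance level. No outside figure is required. An exact binomial test on 60 patients has a discrete rejection region, and its attained size can fall well below the nominal 5%, so its power can be clearly lower than a normal approximation suggests. A figure from an approximate formula would therefore overstate the power of the test that is named.

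The wording is a second, smaller problem. Power is the probability of a significant result given a true rate. An observed rate of 66% is about 40 of 60 (0.66 × 60 = 39.6). That result has a two-sided exact p-value of 0.013, so it is always significant and no 71% probability attaches to it.

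This is the protocol's only power statement and it appears twice. Readers are told that the chance of missing a true rate of 66% is 29% when the named test has a 38% chance of missing it. The wrong figure could also be carried into the analysis plan that Section 7.4.5 defers to.

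**Working it through.** **Inputs, all from Section 7.4.2.** n = 60; null rate p0 = 0.50; alternative p1 = 0.66, read as a true rate; exact binomial test, two-sided, nominal 5%. Section 7.4.1 takes as denominator all patients with at least one dose, so no dropout deduction enters. As a sensitivity value, p1 = 2/3 comes from Section 7.4.

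**Step 1: can 71% be reproduced?** With approximate methods it can:

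- Normal approximation, no continuity correction: Φ((0.16 × √60 − 1.96 × 0.5) / √(0.66 × 0.34)) = Φ(0.2594 / 0.4737) = 0.708.
- Arcsine: Φ((2·asin√0.66 − 2·asin√0.50) × √60 − 1.96) = 0.713.

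**Step 2: critical count of the named test.** For X ~ Binomial(60, 0.5), the two-sided p-value is 2 × P(X ≥ r):

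| r | P(X ≥ r) | Two-sided p |
|---|---|---|
| 37 | 0.0462 | 0.0925 |
| 38 | 0.0259 | 0.0519 |
| 39 | 0.0137 | 0.0273 |
| 40 | 0.0067 | 0.0135 |

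The smallest significant count above 30 is 39, and the attained two-sided size is 2.7%. The null distribution is symmetric, so doubling the tail and the minimum-likelihood definition give the same test. Exact (Clopper-Pearson) 95% intervals confirm the cut-off: 38/60 gives 49.9% to 75.4%, which includes 50%; 39/60 gives 51.6% to 76.9%, which does not.

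**Step 3: power of the named test.**

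- P(X ≥ 39 | p = 0.66) = 0.6227. The lower rejection region adds less than 0.00001.
- P(X ≥ 39 | p = 2/3) = 0.6639.

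Against the stated 71%, the shortfall at 66% is 71.0 − 62.3 = 8.7 points. At n = 60 the exact test reaches 71% only at a true rate of about 0.6745.

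**Step 4: other readings at p = 0.66.**

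| Reading | Power |
|---|---|
| Normal approximation with continuity correction | 66.0% |
| Wald formula | 74.4% |
| Reject at 38 or more (mid-p or uncorrected score test) | 72.0% |
| One-sided exact test at 5% (reject at 37 or more) | 80.2% |

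None of these is the test named. Rejecting at 38 comes close to 71%, but its exact two-sided size is 5.19%, above the nominal level.

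**Step 5: how power moves with n at p = 0.66.** Exact power is 69.3% at n = 58, 62.3% at 60, 68.7% at 61, 71.3% at 63, 68.1% at 64, 70.7% at 66, 70.1% at 69 and 75.4% at 70. It first reaches 71% at n = 63, dips below again, and stays above from n = 70 within the range checked (to n = 74).

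**Step 6: the confidence interval.** The exact interval for 36/60 is 46.5% to 72.4%, which rounds to the 47% to 72% in Section 7.4.2. That figure is right.

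**The case against.** The strongest reply is that nothing turns on the number. Funding set the sample size, the design is a single-group observational cohort, the primary endpoint is a percentage to be estimated, and no stated decision rule uses the test. Both 62% and 71% tell the reader that power is modest. All of this stands and limits the consequence, with one caution: Section 7.4.5 defers details to a later plan, so it shows only that no decision rule is stated here.

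A second reply is that n = 60 is an unlucky point on the saw-tooth of exact power. This is also true, as Step 5 shows. It explains much of the gap, but the sentence is about 60 patients, and at 60 the figure is wrong. It does mean that the error is no evidence that the cohort is materially too small, and that n = 63 should not be read as a threshold.

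A third reply is that 71% could be kept if the approximation were named. That would be internally consistent, but it would no longer describe the exact test that the plan names.

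Finally, a stated cut-off of 39 applies only if exactly 60 patients are treated, and a two-sided test also rejects at 21 or fewer. Both remarks are correct. The first is met by stating the number treated, which agrees with the denominator in Section 7.4.1; the second by tying the cut-off to the conclusion that the rate is higher than 50%.

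**Conclusion.** The concern holds. For 60 patients, a null rate of 50% and a two-sided exact binomial test at 5%, power is 62.3% at a true SVR rate of 66% and 66.4% at two thirds, not 71%. The result assumes that 66% is meant as the true rate and that all 60 patients enter the denominator; every other input is stated in the plan. The most likely explanation is an approximate calculation described as exact, but the documents do not confirm this. It is an error in a stated figure, worth correcting because it is the only power statement and appears twice. It does not affect the sample size, the endpoint or the confidence interval.

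**What to change.** In Section 7.4.2 and in the Project Summary, replace the power sentence with:

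> With 60 treated patients, a two-sided exact binomial test against 50% (nominal type I error 5%) finds the SVR rate higher than 50% at 39 or more SVRs, and has about 62% power if the true SVR rate is 66%.

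This corrects the figure and replaces the observed rate with a true one. Leave the sample size and the confidence interval sentence as they are. The cost is one sentence in two places and a less favourable stated power.
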